4.4.1.1.3 Presence

Presence is derived from the maximum overall intensity on the period considered:

- None: No presence
- Grade 1, Grade 2, or Grade 3: Presence
- Missing: Missing presence

Subjects with at least one non-missing presence for a specific endpoint will be included in the analysis. Conversely, those without a non-missing presence will not be included in the analysis of the endpoint.

4.4.1.1.4 Time of Onset

Time of onset is derived from the daily intensities computed as described in [Section 4.4.1.1.1](#). It corresponds to the first day with intensity of Grade 1, Grade 2, or Grade 3.

Note: If a reaction is not continuous (i.e., reaction occurs over two separate periods of time intervened by at least one daily intensity Missing or None) then the time of onset is the first day of the first occurrence.

Table 4.1: Categories for time of onset

Injection Site and Systemic Reactions (D01-D08)
D01-D04
D05-D08

4.4.1.1.5 Number of Days of Occurrence

Number of days of occurrence over the period considered is derived from the daily intensities computed as described in [Section 4.4.1.1.1](#). It corresponds to the number of days with daily

intensities of Grade 1, Grade 2, or Grade 3. But if a reaction is ongoing at the time of receiving an authorized/approved COVID-19 vaccine, the daily intensities on or after that day will not be considered. Number of days of occurrence on the solicited period with a specified intensity may also be derived.

The number of days of occurrence for safety analysis will treat the date of receiving non-study authorized/approved COVID-19 vaccine as the censored date and only daily intensities that occurred before the vaccination date will be analyzed.

Table 4.2: Categories for number of days of occurrence during the solicited period

Injection Site Reactions (D01-D08)	Systemic Reactions (D01-D08)
1-3 days	1-3 days
4-7 days	4-7 days
8 days	8 days

4.4.1.1.6 Overall Number of Days of Occurrence

If a reaction is ongoing at the end of the solicited period, then the overall number of days of occurrence is derived from the daily intensities and the stop date of the reaction after the end of the solicited period. The overall number of days of occurrence is:

- (stop date – last vaccination date) + (number of days of occurrence within the solicited period) – length of the solicited period + 1

If the stop date is missing or incomplete (contains missing data [MD]), the overall number of days of occurrence will be considered as Missing. If a participant received a non-study authorized/approved COVID-19 vaccine within the solicited period and the solicited reaction is ongoing at the time of the receipt of the authorized/approved COVID-19 vaccine, the overall number of days of occurrence will be analyzed as Missing for main safety analysis.

Table 4.3: Categories for overall number of days of occurrence

Injection Site Reactions (D01-D08)	Systemic Reactions (D01-D08)
1-3 days	1-3 days
4-7 days	4-7 days
8 days or more	8 days or more
Missing	Missing

4.4.1.1.7 Ongoing

Ongoing is derived from the last daily intensity of the solicited period computed as described in [Section 4.4.1.1.1](#) and the maximum intensity in the ongoing period. The Investigator's ongoing flag is not used because the measurement would determine the ongoing status of the reaction.

- Ongoing: if the last daily intensity of the solicited period is at least Grade 1 and the maximum intensity on the ongoing period is at least Grade 1
- Not ongoing: if the last daily intensity of the solicited period is None or the maximum intensity on the ongoing period is None.
- Missing: all other conditions (in this case, it is not included in the denominator of the ongoing analysis in the safety tables).

If a participant received a non-study authorized/approved COVID-19 vaccine within the solicited period, the ongoing status will be derived as “Missing”.

4.4.1.2 Unsolicited AEs

Unsolicited AEs include non-serious unsolicited AEs and SAEs.

4.4.1.2.1 Occurrence

An observation was considered an event if it had at least a verbatim term and was not a Grade 0 intensity event.

Grade 0 events should be included in a separate listing “Unsolicited AEs not included in the safety analysis”.

4.4.1.2.2 Intensity

Intensity for unsolicited AE will be derived according to the following classification: None, Grade 1, Grade 2, Grade 3, or Missing.

If the unsolicited AE is measurable and its preferred term is part of the list of solicited reactions, then the measurement is derived based upon and following the same rule of the intensity scales defined in the protocol for that measurable injection site or systemic reaction.

Note the intensity could be considered “None” (not a reaction) in the analysis despite being considered a reaction by the investigator (e.g., swelling measurement > 0 mm but < 25 mm in adults).

Intensity for the other unsolicited AEs will correspond to the value reported in the eCRF.

The maximum intensity corresponds to the highest intensity for a unique term.

For those participants receiving a non-study authorized/approved COVID-19 vaccine (e.g., on Day X), the maximum intensity of an unsolicited AE is analyzed as following:

- If an unsolicited AE with both time of onset and stop date before Day X, then the maximum

intensity for that AE will be analyzed as collected in CRF.

- If an unsolicited AE with time of onset before Day X and the corresponding stop date is on or after Day X, then the maximum intensity for that AE will be analyzed as Missing.

4.4.1.2.3 Last Vaccination

The last vaccination before an unsolicited AE is derived from the start date of the unsolicited AE provided in the clinical database and is calculated as follows:

- If an unsolicited AE has a complete start date and different to any of the vaccination dates, the start date is used to determine the last vaccination before the unsolicited AE.
- If the start date is missing or partially missing, or equal to any vaccination date, then the visit number in the “Appeared after Visit” or similar field, is used to determine the last vaccination before the unsolicited AE.

4.4.1.2.4 Time of Onset

Time of onset is derived from the start date of the unsolicited AE provided in the clinical database and the date of last vaccination as described in [Section 4.4.1.2.2](#):

Time of Onset = start date of the unsolicited AE – date of last vaccination before the unsolicited AE + 1

The time of onset should be considered as missing only if one or both of the dates are missing or partially missing.

The unsolicited AEs will be analyzed “Within 21 days”, which corresponds to AEs with a time of onset between 1 and 22 days or missing.

An AE with missing time of onset will be considered to have occurred just after the vaccination indicated by the visit number in “Appeared after visit” or similar field, so will be included in these tables.

Time of onset will be displayed as follows:

- D01-D04
- D05-D08
- D09-D15
- D16 or later
- Missing

Note: To further clarify the analysis:

- Any unsolicited AEs reported up to the entire study period (SAEs, MAAEs, AESIs) with time of onset > 22 days after each injection will not be presented in tables of unsolicited AEs within 21 days but only in tables of SAEs, MAAEs, AESIs and NOCMCs.

- Any unsolicited AEs reported up to 21 days with time of onset between 1 and 22 days or missing after each injection will be presented in the tables of unsolicited AEs within 21 days.
- Any unsolicited AEs reported up to 21 days with time of onset > 22 days after each injection will not be presented in any tables but listed separately.
- Any unsolicited AEs with null (0) or negative time of onset will be excluded from the above tables and listed separately

Safety analysis will include only those unsolicited AEs with time of onset before a participant received a non-study authorized/approved COVID-19 vaccine if applicable. Events with time of onset on or after the date of receiving a non-study authorized/approved COVID-19 vaccine will be listed separately.

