5.3.1.5 Start Date and Stop Date

Missing or partially missing start dates for unsolicited AEs will remain missing and not be imputed. If either the start or stop date is missing or partially missing, the time of onset will be considered to be missing. Nevertheless, unsolicited AEs with missing time of onset will be included in analyses according to the visit collected.

Missing or partially missing stop dates for AEs (solicited reactions and unsolicited AEs) will remain missing and not be imputed.

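### Unsolicited AEs with an incomplete start date default into the 21-day safety tables without a check against a known month or the visit number, so demonstrably late events can be counted there

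*SAP*

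**What the plan says.** SAP 4.4.1.2 includes SAEs among the unsolicited AEs, so the rules below apply to them.

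- **Onset formula (SAP 4.4.1.2.4).** "Time of Onset = start date of the unsolicited AE – date of last vaccination before the unsolicited AE + 1".
- **When onset is missing (SAP 4.4.1.2.4).** "The time of onset should be considered as missing only if one or both of the dates are missing or partially missing". SAP 5.3.1.5 adds that incomplete start dates are not imputed.
- **The 21-day window (SAP 4.4.1.2.4).** The analysis is of events within 21 days, "which corresponds to AEs with a time of onset between 1 and 22 days or missing".
- **Placement of missing onset (SAP 4.4.1.2.4).** "An AE with missing time of onset will be considered to have occurred just after the vaccination indicated by the visit number" held in the *Appeared after Visit* field or a similar one. The sentence ends by putting these events in the 21-day tables.
- **Use of the visit number (SAP 4.4.1.2.3).** If the start date is incomplete, the visit number "is used to determine the last vaccination before the unsolicited AE".
- **The Note in SAP 4.4.1.2.4.** One bullet begins "Any unsolicited AEs reported up to the entire study period (SAEs, MAAEs, AESIs) with time of onset > 22 days after each injection will not" and keeps those events out of the 21-day tables. The next begins "Any unsolicited AEs reported up to 21 days with time of onset between 1 and 22 days or missing after each injection will be presented" and places those events in them.
- **SAP 5.3.1.5.** "Nevertheless, unsolicited AEs with missing time of onset will be included in analyses according to the visit collected".

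**The concern.** Treating an undatable event as early is a sensible conservative convention. The difficulty is that the SAP applies it even when recorded data contradict it. A start date with only the day missing is handled exactly like a wholly unknown date, although the month alone may place onset well beyond day 22.

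Unsolicited AEs up to 21 days after each injection are a primary safety endpoint (protocol Table 3.1). SAP 5.1.1.2 also tabulates SAEs and AESIs within 21 days. Events first reported long after vaccination will mostly be SAEs, AESIs and MAAEs, because other unsolicited AEs are collected only for 21 days after each injection. If one of these is counted as acute, the short-term profile of a small arm changes. Programmers could also build different tables from the same text, because its statements on missing onset are not reconciled.

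**Working it through.** The plan states no figure that depends on this rule, so there is nothing to reproduce. The check traces the rule and then applies it to the visit schedule.

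**1. Trace an event with month and year known but day missing.** The start date is partial, so onset is missing (4.4.1.2.4). It is not imputed (5.3.1.5). The visit number selects a vaccination (4.4.1.2.3). There are at most two injections, so any later visit points back to the last one. The window accepts missing onset, so the event enters the 21-day table. No step asks whether day 22 or earlier is possible.

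**2. See whether other text stops this for whole-study events.**
- The first Note bullet removes SAEs, MAAEs and AESIs only if onset exceeds 22. A missing onset does not exceed 22.
- The second bullet sends missing onset to the 21-day tables only for AEs reported up to 21 days. It says nothing about whole-study events.
- The 5.3.1.5 sentence can mean the period in which the visit falls, which would keep late events out. It can also mean the vaccination that the visit indicates, which would let them in.

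The treatment of these events is therefore undefined, and the general sentence in 4.4.1.2.4 lets them in.

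**3. Ask what the visit number could show.** Inputs are the intervals in SAP Tables 3.1 and 3.2. Nominal onset day = days since last injection + 1.

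| Visit | Cohort 1 | Cohort 2, after second injection |
|---|---|---|
| V03 | 21 + 1 = 22 | 8 + 1 = 9 |
| V04 | 35 + 1 = 36 | 14 + 1 = 15 |
| V05 | 112 + 1 = 113 | 112 + 1 = 113 |
| V06 | 180 + 1 = 181 | 180 + 1 = 181 |

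The visit windows only extend forward, so an in-window visit is never earlier than these days. An event that appeared after V04 or later in Cohort 1, or after V05 or later in Cohort 2, began after day 22. Cohort 1 V03 is borderline, and Cohort 2 V03 and V04 are compatible with the window, so these keep the default.

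**4. Ask what a known month could show.** The earliest possible onset is the first day of that month. If (first day of month − date of last vaccination + 1) exceeds 22, the event cannot belong in the window.

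**5. Exposure.** With follow-up to day 366 after the last injection, (366 − 22)/366 = 344/366, or 94% of that time, lies outside the window. This shows that late events are possible. It does not show how many have incomplete dates.

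**6. Effect of one misplaced participant.** Illustration only: an arm with no event in the row goes from 0/n to 1/n, with exact Clopper-Pearson 95% intervals (the SAP's method).

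| n | 0/n | 1/n |
|---|---|---|
| 10 | 0% (0 to 30.9) | 10% (0.3 to 44.5) |
| 20 | 0% (0 to 16.8) | 5% (0.1 to 24.9) |
| 30 | 0% (0 to 11.6) | 3.3% (0.1 to 17.2) |
| 60 | 0% (0 to 6.0) | 1.7% (0.04 to 8.9) |
| 90 | 0% (0 to 4.0) | 1.1% (0.03 to 6.0) |

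By protocol Table 4.2, arms within an age group have 10, 20, 30 or 60 participants. The two-injection AS03 arms pooled over age have 90.

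**The case against.** The strongest reply is that the SAP, read as a whole, may already do the right thing. The Note exists to clarify the analysis, and it ties missing onset to AEs reported up to 21 days. SAP 5.3.1.5 can be read as placing events by visit period. This stands to the extent that a reader who concluded that late events always enter the 21-day tables would go too far. It does not settle the matter, because neither text says where a whole-study event with missing onset goes.

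Second, incomplete dates should be uncommon. SAEs are reported within 24 hours, AESIs follow the same expedited route, staff interview participants about diary entries, and a data review precedes database lock. This is fair and limits the expected number. Non-serious MAAEs do not have the expedited route unless they are also AESIs.

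Third, the CRF is not available. If the *Appeared after Visit* field records only vaccination visits, it cannot reveal a late event. This stands, and the visit-number check must be conditional on it. The known-month check does not depend on that field.

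Fourth, the effect is visible and nothing is lost. Missing onset has its own display category, and SAEs, AESIs and MAAEs also have 6-month, 12-month and whole-study tables. This stands, though the participant still counts in the 21-day total.

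A reader might also infer that the default would attribute to study vaccine an event that began after an outside COVID-19 vaccine. The documents do not support that. SAP 4.4.1, 5.1 and 5.1.1.2 restrict the analysis to safety data collected before the outside vaccine, and an event that began after it must have been collected after it.

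**Conclusion.** The concern holds as a gap in a stated rule. SAP 4.4.1.2.4 counts incompletely dated events as early without using information that could show otherwise, and the text on whole-study events is unreconciled. Demonstrably late SAEs, AESIs and MAAEs can therefore enter the 21-day tables.

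The documents do not give the number of late events or the share with incomplete dates, so no count can be stated. The increase of 10, 5 or 3.3 points per misplaced participant in arms of 10, 20 or 30 assumes that the participant has no other AE in the window, because the tables count participants. The first interim analysis uses safety data up to D43, so the effect would fall mainly on the 6-month and final analyses. All analyses are descriptive and no test is affected. Severity is minor.

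**What to change.** Amend SAP 4.4.1.2.4 so that an AE with a missing or partial start date is counted within 21 days unless one of the following shows onset after day 22:

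- the known part of the start date; or
- the *Appeared after Visit* number, where that field records non-vaccination visits (V04 or later in Cohort 1, V05 or later in Cohort 2).

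State that SAEs, AESIs and MAAEs excluded in this way stay in their follow-up-period tables. Truly undatable events keep the present default.

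Align 5.3.1.5 by replacing its sentence on the visit collected with a reference to this rule. That section also makes onset missing when only the stop date is incomplete. This conflicts with 4.4.1.2.4, whose onset formula does not use the stop date, and it should be reconciled in the same edit.

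The cost is a sentence in each section and one programming condition. The date check uses data already collected. The visit check needs one look at the CRF to confirm what the field holds.

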4.4.1.2.5 Duration

Duration is derived from the start and end dates of the unsolicited AE:

Duration = stop date of unsolicited AE - start date of unsolicited AE + 1.

The duration should be considered as missing only if one or both of the start and end dates of the unsolicited AE is missing or partially missing.

For those participants receiving a non-study authorized/approved COVID-19 vaccine (e.g., on Day X), the duration is categorized as following:

- If an unsolicited AE with both time of onset and stop date before Day X, then the duration for that AE will be derived same as above.
- If an unsolicited AE with time of onset before Day X and the corresponding stop date is on or after Day X, then the duration will be derived as Missing.

Duration will be displayed by period as following:

- 1-3 days
- 4-7 days
- 8 days or more
- Missing

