5.1.1.2 Statistical Methods for Primary Safety Objective

Safety results will be described for each age and vaccine group. The homogeneity of pooled groups will be assessed on the main parameters. The main parameters will be described with 95% CI.

Safety analyses will be performed based on safety analysis set including safety data collected before the date of receiving an authorized/approved COVID-19 vaccine. Safety data collected on or after the day of receiving an authorized/approved COVID-19 vaccine will be listed separately.

Solicited Reactions

Number and percentage of subjects with:

- Presence of solicited injection site reactions and systemic reactions occurring up to 7 days after injection
- Each solicited reaction according to time of onset, maximum intensity, and number of days of occurrence over the solicited period

Unsolicited Events and Reactions

Number and percentage of subjects with:

- Any unsolicited immediate systemic event in the 30 minutes after injection
- Any unsolicited event and reaction (using the current MedDRA version) 21 days after injection
- Any unsolicited event/reaction according to time of onset, maximum intensity, and duration

SAEs

Number and percentage of subjects with:

- any SAE within 21 days after injection and during the 6 months and 12 months follow-up periods according to SOC and PT, seriousness and outcome

AEs of special interest

- Number and percentage of subjects with any/each AESI within 21 days after injection and during the 6 month and 12 months follow-up periods will be presented according to SOC and PT, seriousness and outcome.

MAAE

- Presence of medically attended adverse events (MAAEs) throughout the study

Laboratory tests

- Presence of out-of-range biological test results up to 7 days post-last dose (ie, up to D09 for Cohort 1 and up to D30 for Cohort 2)

The following analyses will be performed for laboratory tests in addition to the summary of out of range tests above:

- Biological test results and toxicity grade by visit,

- Summary of toxicity grade shift from baseline,

For descriptive purposes, the statistics presented on [Table 5.1](#) will be produced.

In addition to analyses by each intervention group, aggregated groups will be used to perform complementary assessments for above parameters, including:

1. aggregated vaccine group, ie, all vaccine arms pooled
2. aggregated placebo group, ie, two placebo arms pooled

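### Unsolicited adverse events with no complete stop date are tabulated as Missing duration even when they are already known to have lasted 8 days or more

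*SAP*

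**What the plan says.** SAP 4.4.1.2.5 defines "Duration = stop date of unsolicited AE - start date of unsolicited AE + 1". The missing-data rule follows: "The duration should be considered as missing only if one or both of the start and end dates of the unsolicited AE is missing", and the sentence goes on to include partially missing dates. The rule makes no exception for an event that is simply ongoing. The section then sets the display ("Duration will be displayed by period as following"): 1-3 days, 4-7 days, 8 days or more, Missing.

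A separate rule covers a participant who receives a non-study COVID-19 vaccine on Day X. If the event began before Day X and "the corresponding stop date is on or after Day X, then the duration will be derived as Missing".

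SAP 5.3.1.5 closes off any other route: "Missing or partially missing stop dates for AEs (solicited reactions and unsolicited AEs) will remain missing and not be imputed".

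The solicited-reaction counterpart is in SAP 4.4.1.1.6, which feeds Table 4.3: "If the stop date is missing or incomplete (contains missing data [MD]), the overall number of days of occurrence will be considered as Missing".

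Duration is used in SAP 5.1.1.2, under the primary safety objective, which lists "Any unsolicited event/reaction according to time of onset, maximum intensity, and duration". SAP 4.4.1.2 adds that "Unsolicited AEs include non-serious unsolicited AEs and SAEs", so an SAE with onset in the window can appear in this table.

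**The concern.** The top duration category has no upper limit. Placing an event there requires proof only that it lasted at least 8 days. An event with a known start date that was still open at a contact 8 or more days later meets that test without a stop date.

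As written, an event that resolved on its eighth day counts as 8 days or more, while one still open after a year does not. The reason the stop date is absent is often that the event is long, so the error runs one way: the prolonged row can only be too small. A reader also cannot tell, within the Missing row, an event known to be long from one whose dates were not recorded.

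At stake is the accuracy of a descriptive breakdown listed under the primary safety objective, in arms small enough that one participant shifts a percentage visibly.

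**Working it through.** The documents give no figure for this point, so there is none to reproduce. The check applies the SAP rules to hypothetical events and compares each result with what is already known about the event.

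**Inputs.** Formula, missing rule, Day X rule and categories: SAP 4.4.1.2.5. No imputation: SAP 5.3.1.5. Solicited formula and Ongoing status: SAP 4.4.1.1.6 and 4.4.1.1.7. Arm sizes: protocol Table 4.2. The event dates are assumed, with onset on 1 October 2020.

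**Unsolicited AEs.** Known minimum duration = last date on which the event is known to be present (or earliest possible stop date) - start date + 1.

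| Event | SAP result | Known minimum | Row it belongs in |
|---|---|---|---|
| Stops 2 October | 2 days | 1 + 1 = 2 | 1-3 days |
| Stops 8 October | 8 days | 7 + 1 = 8 | 8 days or more |
| Open at last contact, 12 November | Missing | 42 + 1 = 43 | 8 days or more |
| Open at 1 October 2021 | Missing | 365 + 1 = 366 | 8 days or more |
| Partial stop date, December 2020 (earliest 1 December) | Missing | 61 + 1 = 62 | 8 days or more |
| Stops 20 November, Day X is 31 October (count to 30 October) | Missing | 29 + 1 = 30 | 8 days or more |

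The SAP classifies the two resolved events correctly and sends the other four to Missing.

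**First interim.** On nominal days, an event with onset on day d that is known to be open at D43 has lasted at least 43 - d + 1 days. This is 8 or more whenever d is 36 or earlier. Such an event can be classified at that cut without a stop date.

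**Solicited reactions.** Overall days = (stop date - last vaccination date) + days of occurrence in the solicited period - length of that period + 1. A reaction present on all 8 days that stops on D09 gives 8 + 8 - 8 + 1 = 9. One that stops a day later gives 9 + 8 - 8 + 1 = 10. The same reaction with no complete stop date is Missing in Table 4.3. Yet if it is Ongoing under SAP 4.4.1.1.7 (at least Grade 1 on the last solicited day and again in the ongoing period), it has lasted at least 8 + 1 = 9 days. A reaction present on 7 solicited days and Ongoing has reached 7 + 1 = 8.

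**Possible size (assumed counts).** Take 20 events, of which 8 truly last 8 days or more (40%), and let a share of those 8 have no usable stop date.

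| Share without stop date | Top row, of 20 | Missing row | Top row if Missing is left out of the denominator |
|---|---|---|---|
| 0% | 8 (40%) | 0 | 8/20 = 40% |
| 25% | 6 (30%) | 2 | 6/18 = 33% |
| 50% | 4 (20%) | 4 | 4/16 = 25% |
| 75% | 2 (10%) | 6 | 2/14 = 14% |
| 100% | 0 (0%) | 8 | 0/12 = 0% |

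The SAP percentages are of subjects. With all subjects in the arm as denominator, each affected participant with no other event in the top row lowers it by 1/n: 10 percentage points for n = 10, 5 for n = 20, 3.3 for n = 30 and 1.7 for n = 60, the planned arm sizes within age group.

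**The case against.** The strongest reply is that little is hidden and nothing is decided on this row.

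- **Nothing is dropped.** Missing is a displayed row, and the event stays in the AE counts. This stands. The fault is misplacement, not removal.
- **Chronic disease is reported elsewhere.** A reader might infer that new-onset chronic conditions and immune-mediated diseases disappear from the safety results. The documents do not support that. SAP 5.1.1.2 tabulates SAEs and AESIs by system organ class and preferred term, seriousness and outcome, not by duration. SAP 4.4.1.4.7 follows AESIs to 12 months. Under SAP 4.4.1.2.4, only events with onset on days 1 to 22 after an injection, or with missing onset, enter the within-21-days tables.
- **Solicited reactions are largely covered.** A reaction present on all 8 days has its own row in Table 4.2, and SAP 4.4.1.1.7 derives an Ongoing status that needs no stop date. SAP 5.1.1.2 names the Table 4.2 quantity, not the Table 4.3 one. This stands and makes the solicited part secondary.
- **No rule turns on duration.** The primary safety endpoints are the presence of events, the early safety review and halting rules do not use duration, and all analyses are descriptive. A reader might also infer that formulation selection at the D43 interim is distorted. That interim does use safety data, but neither protocol 9.5 nor SAP 5.4 names duration as an input, and no count of open events is given.
- **Some end dates will arrive.** Protocol 8.4.3 has related AEs, and those causing discontinuation, followed to resolution, stability or chronicity, with a date reported. The SAP does not link a chronicity date to duration, so this helps only in part.

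These points limit the consequence. None supplies a rule that places an open unsolicited AE in the right row, and SAP 4.4.1.1.7 has no counterpart for unsolicited AEs. A separate Ongoing row would help, but it would not resolve partial stop dates or events that cross Day X.

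**Conclusion.** The point holds for unsolicited AEs. SAP 4.4.1.2.5 with 5.3.1.5 gives Missing duration to an event whose known minimum is already at least 8 days. The top row is understated by the number of such events or, when subjects are counted, by at most that number. The direction is certain wherever such an event occurs. The size cannot be stated, because the documents do not say how many events will lack a complete stop date; the 20-event table is an illustration only.

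The effect is confined to descriptive duration rows: mainly the within-21-days unsolicited AE table, and secondarily Table 4.3. AE counts and the SAE and AESI tables are not affected. The conclusion assumes that the start date is complete and that a dated contact shows the event still open. It is a modest fault in a primary safety table, worth correcting because correction is cheap.

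**What to change.** Add to SAP 4.4.1.2.5, with a cross-reference in 5.3.1.5 stating that no date is imputed and only the category is assigned:

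- For an unsolicited AE that is ongoing, has a partial stop date, or crosses Day X, compute minimum duration = end point - start date + 1. The end point is the earliest of last contact, data cut and the day before any non-study COVID-19 vaccine; if the stop date is partial, the earliest possible stop date is added to that list.
- If the minimum is at least 8, classify as 8 days or more. Otherwise keep Missing. An event without a complete start date also stays Missing.

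Ending the count before Day X keeps the rule consistent with SAP 4.4.1 and 5.1, which exclude data from that date on. It also follows SAP 4.4.1.1.5, which already treats the vaccine date as a censoring date for solicited reactions.

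For Table 4.3, classify as 8 days or more when the reaction is Ongoing under SAP 4.4.1.1.7 and days of occurrence in D01-D08 plus 1 is at least 8, provided the added day also falls before any non-study vaccine.

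Cost: a few lines of SAP text, slightly more programming and no new data. The top row will then rest partly on minimum rather than exact durations, which a table footnote should state.
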